Phase I Single Ascending Dose Study (SAD): A double-blind, placebo-controlled, ascending, single-dose safety, tolerability, and pharmacokinetic study of SRX246 in capsules was undertaken in healthy adult volunteers. A total of 49 Subjects were enrolled—37 males and 12 females with a mean age of 43.5 years. The Subjects were representative of different races: Caucasian (7), black/non-Hispanic (23), Hispanic (18), Asian/Pacific Islander (1). A single oral dose of SRX246 was administered to a total of 34 Subjects enrolled in a total of 7 separate cohorts. The dosing cohorts were as follows: 20 mg (5 Subjects), 80 mg (2 consecutive cohorts of 5 Subjects each), 160 mg (5 Subjects), 240 mg (5 Subjects), 320 mg (4 Subjects). There were a total of 15 placebo Subjects spread among all cohorts (2 per cohort except for Cohort 7 in which there were 3). All Subjects completed the study; there were no SAEs, deaths, or discontinuations.

Safety summary: A total of 25 adverse events (AEs) were recorded. Overall, no trend was identified in terms of specific organ system affected with increasing dose. In fact, the placebo Subjects experienced a higher absolute number of AEs than the experimental Subjects except for orthostatic tachycardia (OT), which is discussed below. In Cohort 1 (20 mg) a single AE (mild light headedness) was reported. There were no AEs reported in Cohort 2 (40 mg). In Cohort 3 (80 mg) elevations in heart rate (HR) immediately upon standing were described in 3 patients. At the time these events were observed, some of the HR readings were repeated manually; the elevation in HR could not be confirmed, and the “tachycardia” was not accompanied by any clinical symptoms. Nonetheless, the 80 mg dose was repeated in a new cohort of Subjects prior to dose escalation. In this new group of Subjects, there was no orthostatic tachycardia (OT) and no other AEs.

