6.6 Visit 03 (Week 8) Day 56±5

The following procedures will be performed during this visit (this visit may take about 4 hours):

- Assess the Subject for possible AEs and Concomitant Medication use.
- Review amount of study drug returned and assess compliance.
- Review the use of the eDiary and encourage the Subject and Study Partner to make and upload entries two times per day.
- Perform orthostatic vital sign measurements: blood pressure (systolic and diastolic) and heart rate (beats/minute).
- Record the Subject's body temperature (°C).
- Perform a resting 12-Lead EKG.
- Collect blood samples for routine hematology/serum chemistry (refer to Section 6.13.5 for required tests).
- If two tubes not collected at Baseline Visit (Day 0), collect blood samples for CAGn genotyping and/or DNA storage (refer to University of Rochester Medical Center Lab Manual for sample handling and processing requirements).
- Collect urine for routine urinalysis (refer to Section 6.13.5 for required tests).
- Prepare the subject for PK blood sampling for the sparse PK study. Subjects will have been prompted to note the time at which the dose of study compound was taken the night before (either in their eDiaries or on a piece of paper), and to bring their dose for the morning of the visit with them but not to take it until they are instructed to do so.
 - Blood will be drawn as soon as the patient arrives in the clinic; then the morning dose of drug should be given and the time recorded.
 - Perform orthostatic vital sign measurements: blood pressure (systolic and diastolic) and heart rate (beats/minute) approximately 1-2 hours after taking the morning dose (estimated time to Cmax).
 - Two (2) hours later (time to be recorded), blood will be drawn again.
 - Process the PK samples as directed in the University of Rochester Medical Center Lab Manual
- Dispense study drug and instruct the Subject and Study Partner about correct administration of study drug (i.e., either 120 mg BID SRX246, 160 mg BID SRX246 or Placebo, or possible dose reduction based on intolerance).
- Instruct Subject and Study Partner to bring unused study drug to each visit, and to immediately report any AEs to the Investigator or Coordinator.

- If not performed during this Visit, at the time of scheduling the next visit, remind the Subject not to take drug (or placebo) on the morning of the next visit, that the study drug will be taken in the clinic during the next visit to enable sparse PK sampling.

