6.12.1 Dosage Reduction

Dosage reductions are permitted during the study due to tolerability issues or adverse events that are thought to be related to study drug. In the first two weeks of the trial, subjects who cannot tolerate the drug will receive no more capsules but will be encouraged to continue participating in the study. Reductions can be performed once between study weeks 2 and 6, and twice between study weeks 6 and 12. The project manager should be notified in this case to discuss and confer with the protocol PI and/or medical monitor if necessary. A dosage reduction is accomplished by lowering the total daily dose (as deemed necessary by the site Investigator) until symptoms resolve or reduced dosage is tolerated by the Subject. Dose reduction can only be performed up to a maximum of 2 times, until the Subject is removed from further dosing with study drug.

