6.13.7 Sparse Sampling Population PK of SRX246

Blood samples will be obtained periodically throughout the study for Sparse PK Sampling. Subjects will be prompted to note the time at which the dose of study compound is taken the night before in their eDiaries, and to bring their dose for the morning of the visit with them but not to take it until they are instructed to do so. Blood will be drawn as soon as the patient arrives in the clinic and the time of the blood draw will be recorded; then the morning dose of drug should be given and the time recorded. Two (2) hours later (time to be recorded), blood will be drawn again.

Objectives of the population pharmacokinetic analysis: 1) To characterize the population pharmacokinetics of SRX246 comparing sparse sampling data from Subjects with Huntington's Disease with detailed Phase 1 clinical trial pharmacokinetic assessments in healthy volunteers; and, 2) To identify patient-specific characteristics (e.g., age, gender, weight, disease severity) that may influence the PK parameter estimates of SRX246 in these populations.

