Data to be included: 1) Individual SRX246 plasma concentrations from Study No. AVN005 (single-dose PK of 20, 40, 80, 160, and 320 mg oral doses in 33 healthy Subjects (Azevan Pharmaceuticals, Clinical Study Report for AVN005, Phase 1, Double-Blind, Placebo-Controlled, Ascending, Single-Dose, Safety, Tolerability, and Pharmacokinetic Study of SRX246 Capsules in Healthy Volunteers); 2) Individual SRX246 plasma concentrations from Study No. AVN007 (multiple-dose PK of 30, 60, 120 mg twice-daily doses given for 14 days in 18 healthy Subjects (Azevan Pharmaceuticals, Clinical Study Report for AVN007, Phase I, Double-Blind, Placebo-Controlled, Ascending, Multiple-Dose, Safety, Tolerability and Pharmacokinetic Study of SRX246 Capsules in Healthy Adult Volunteers.), and 3) Plasma concentrations of SRX246 obtained before (C_{min}) and at approximately 2 hours (C_{max}) after oral doses of 120 and 160 mg twice-daily given for at least 14 days in Subjects with Huntington's Disease. (N.B. The times at which SRX246 is taken the evenings before the C_{min} determinations are made will be recorded by Subjects or their care givers. The times at which blood samples are drawn in the clinic the next morning will also be recorded. This, and the C_{max} levels estimated by measuring SRX246 in the blood approximately 2 hours after Subjects take their morning dose of drug, will allow us to determine t_{1/2} reasonably accurately.) Possible covariates to be evaluated include: body size, age, gender, and disease severity.

Data Input Format: The NONMEM data file requires Subject number, times of the doses, dose amounts, times of the plasma samples, plasma concentrations, values of covariates such as body size, age, etc. All data related to one patient, including dosage information, must be in chronological order. Data files will be constructed by use of automated data processing based on csv-files provided by the analytical company. At least 10% of the dataset will be checked manually.

Missing Data: For missing concentrations due to a concentration falling below the quantification limit of the bioanalytical assay the method of omitting these data points (Beal M1) and the Beal M3 method will be considered (Beal 2001).

Data Analysis Methods: Software: NONMEM version 7.3.0 (Icon Development Solutions, [name]). Self-written differential equations will be solved using the ADVAN6 PREDPP subroutine.

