8 GENERAL DESIGN ISSUES

The study design consists of three parallel arms: placebo and two final doses of SRX246 (120 mg BID and 160 mg BID). Thirty-six patients will be randomized into each study arm. Since we have only given SRX246 to generally healthy subjects thus far, and since some HD patients may be frailer population, we have elected to initiate treatment at 80 mg BID; to increase the dose of drug to 120 mg BID after two weeks in those patients who have tolerated the starting dose; and to increase the dose of drug again after 2 additional weeks in those patients who are taking 160 mg BID. Subjects in the placebo group will take capsules that will be identical in appearance to those containing SRX246. Thus, patients and study staff will both be blind to treatment, and twice as many Subjects will receive active agent as placebo. The placebo group will be used for comparison with each active drug group.

Subjects who are unable to increase their dose of drug can remain in the study at the highest dose they can tolerate, and Subjects who find the drug intolerable can reduce the dose of drug (to 80 mg BID of SRX246 or placebo, but no lower without dropping out of the study). The goal is to study the behavioral scales in as many people as possible because we feel that this will be important to the clinical research community.

At the end of the trial, data from all Subjects who were given placebo will be combined, and two pairwise tests will be performed (120 mg vs placebo, 160 mg vs placebo--see below).

It may be necessary to screen as many as 150 candidates to enroll 108 Subjects. Up to 20 NeuroNEXT sites may participate in the study, with each site's goal to enroll about 5-6 Subjects within the first 18 months of the trial.

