- b – Conduct pre-dosing and 1-2 hours post first dose of administering study medication.
- c – Return all study drug supplies to clinic, do not issue additional study drug
- d - If not performed during Week 8, perform at Week 10.
- e – Review and re-administer if study partner changes
- f – If two tubes not collected at BL, ensure two tubes are collected by Week 12 (Visit 05)

R –Review; (s) – Serum test; (u) – Urine test

Definitions for Study Weeks/Visits: SC – Screening; BL – Baseline; T – Telephone Contact; F/U – Follow-up

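### Read literally, the definition of the HD population-PK dataset drops samples the trial already draws: those on 80 mg BID, and those taken fewer than 14 days after the step to 160 mg BID

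*Protocol*

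**What the plan says.** - **Dataset.** Item 3 of the data list in protocol section 6.13.7 admits HD concentrations taken before and about 2 hours after dosing, "after oral doses of 120 and 160 mg twice-daily given for at least 14 days". No other definition is given; the SAP text supplied does not describe the population-PK analysis.
- **Reduced doses.** Section 8 states: "Subjects who find the drug intolerable can reduce the dose of drug (to 80 mg BID of SRX246 or placebo". Section 6.5 allows a reduction at week 6, so a participant can reach the week 8 PK visit already reduced. Section 6.6 sets no dose condition on PK sampling, and its dispensing step covers "either 120 mg BID SRX246, 160 mg BID SRX246 or Placebo, or possible dose reduction based on intolerance".
- **Sampling times.** Section 6.13.7 opens with "Blood samples will be obtained periodically throughout the study for Sparse PK Sampling". Sections 6.6 and 6.7 describe one occasion, at week 8 with week 10 as fallback. Appendix A, footnote d, agrees: "If not performed during Week 8, perform at Week 10".
- **Early stops.** Under section 6.12.1, in the first two weeks "subjects who cannot tolerate the drug will receive no more capsules but will be encouraged to continue participating in the study". Section 6.12.4 permits a restart if the stop was unrelated to safety.
- **Model input.** Section 6.13.7 already requires dose amounts, dose times and sample times in the NONMEM file.
- **Phase I data.** Section 6.13.7 lists AVN005 as "single-dose PK of 20, 40, 80, 160, and 320 mg oral doses in 33 healthy Subjects". Section 2.2 reports 34 subjects on active drug in the single-dose study, with cohorts that include "240 mg (5 Subjects), 320 mg (4 Subjects".

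**The concern.** The first population-PK objective compares HD participants with healthy volunteers. In a trial whose primary endpoint is tolerability, participants who had to reduce their dose are among the most informative about HD exposure. If their samples are drawn and then left out, the analysis loses data and conditions the HD sample on having stayed at 120 mg BID or above. If high exposure caused the reduction, HD would look more like healthy volunteers than it is. The 14-day minimum also removes 160 mg samples for scheduling reasons alone. Because the wording can be read in two ways, the choice would be made after the data are in hand.

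**Working it through.** The plan gives no PK sample size, precision or loss rate, so there is no stated figure to reproduce.

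**1. Who is in the dataset on a literal reading**

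| State at the PK visit | Sampled on drug? | In dataset? |
|---|---|---|
| 120 mg arm, on 120 mg | Yes | Yes |
| 160 mg arm, on 160 mg | Yes | Only if at least 14 days |
| 160 mg arm, reduced to 120 mg | Yes | Yes, subject to the 14 days |
| Either arm, on 80 mg | Yes | No |
| Stopped before week 8, not restarted | No | No |
| Stops after the PK sample | Yes | Yes |

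**2. The 14-day minimum.** The step to 160 mg is at week 6 (day 42±5: days 37–47) and the PK visit at week 8 (day 56±5: days 51–61).
- Time on 160 mg: 51 − 47 = 4 days to 61 − 37 = 24 days.
- If each visit day is uniform and independent over its window (assumption), there are 11 × 11 = 121 pairs. The minimum is met when the week 8 offset is no smaller than the week 6 offset: 66 pairs, or 55%.
- If all 36 in the 160 mg arm were sampled at week 8, about 36 × 66/121 = 19.6 would count. The standard error of a simple arm mean would grow by √(121/66) = 1.35. Visits booked a fixed 14 days apart would lose fewer.
- At the week 10 fallback the range is 65 − 47 = 18 to 75 − 37 = 38 days, so all qualify.

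This uses the week 6 step of sections 2.1.3, 3 and 6.5. Section 8 instead puts the step two weeks after the move to 120 mg, and those passages must be reconciled. A step at day 28±5 would give at least 51 − 33 = 18 days, and the minimum would not bite.

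**3. How many might be affected.** There are 72 active participants. Treatment completion in protocol Table 4 runs from 78% to 91%, so non-completers for any reason would number 72 × 0.09 = 6.5 to 72 × 0.22 = 15.8. At the planning bound of 0.80 − 0.20 = 0.60 the figure is 72 × 0.40 = 28.8. Only an unstated part of these would be on 80 mg or stopped before week 8.

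**4. Spread of exposure.** Assume the intervals in protocol Tables 1 and 3 come from a straight line fitted to 6 subjects at 60 mg and 6 at 120 mg (mean dose 90, Sxx = 12 × 900 = 10,800, t = 1.8125 on 10 df). For day 14 Cmax:
- at 120 mg: s = 88.05 / (1.8125 × √(1/12 + 900/10,800)) = 119.0 ng/mL
- at 160 mg: s = 158.1 / (1.8125 × √(1/12 + 4,900/10,800)) = 119.0 ng/mL

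The agreement supports the assumption. The CV at 120 mg is 119.0/229.1 = 52%. The same method gives 43% for day 14 AUC, and 31% and 38% for day 7 Cmax and AUC.

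**5. Possible bias in dose-adjusted exposure.** Take lognormal exposure with CV 50%, so σ = √ln(1.25) = 0.472. Let the log-odds of exclusion be linear in standardised log exposure x. The bias in the geometric mean is exp(σ × mean of x among those retained) − 1. If exactly the highest fraction f is removed, it is exp(−σφ(z)/(1 − f)) − 1, where z is the 1 − f normal quantile. For f = 0.10 this is exp(−0.472 × 0.1755/0.90) − 1 = −8.8%.

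| Exclusion and exposure | 10% excluded | 20% excluded |
|---|---|---|
| OR 0.5 per SD | +3.0% | +6.1% |
| Unrelated | 0 | 0 |
| OR 2 per SD | −3.2% | −6.0% |
| OR 3 per SD | −4.6% | −8.5% |
| Highest exposures removed exactly | −8.8% | −15.2% |

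At CV 30% the OR 2 to 3 range is −2.0% to −5.4%. The fractions and odds ratios are assumptions.

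**6. Unadjusted mean.** The Table 3 line puts day 14 Cmax at 80 mg at 33.2 + 20 × (229.1 − 33.2)/60 = 98.5 ng/mL. An equal mix of 120 and 160 mg averages (229.1 + 359.6)/2 = 294.4. With 5% on 80 mg, leaving them out raises the raw mean by 294.4/(0.05 × 98.5 + 0.95 × 294.4) − 1 = 3.4%; with 20% it is 15.3%. So the raw mean moves up.

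**7. AVN005 count.** The cohort sizes printed in section 2.2 sum to 5 + 10 + 5 + 5 + 4 = 29. The 40 mg cohort, named only in the safety summary, accounts for the other 34 − 29 = 5. Without 240 mg the total is 34 − 5 = 29. Neither 34 nor 29 equals 33.

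**The case against.** Item 3 states no exclusion rule and may simply describe the planned doses. The 14 days may be meant to count time on 120 and 160 mg together, in which case the windows cost nothing. The NONMEM file already takes actual doses and times, and population PK is exploratory. All of this is fair, and the analysts may well intend to use every sample. But this is the only definition of the dataset, and it does not say so.

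A reader might infer four stronger things that the documents do not support.

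- **That HD exposure will be biased low.** This needs intolerance to rise with exposure. Sections 2.3 and 7 report adverse events as not dose related. In the multiple-dose study, likely-related events were about 25% on placebo, 30 mg and 60 mg BID, and none on 120 mg BID. That evidence is thin: six subjects per dose for 14 days, 15 men for about a week in the imaging study, and no earlier use of 160 mg BID. It leaves the direction open.
- **That exposure cannot be linked to intolerance.** Participants reduced from 160 to 120 mg, and those who stop after the PK sample, can be in the dataset, and both are non-completers under SAP section 2. A partial link is possible, although no exposure–tolerability analysis is planned.
- **That one HD occasion defeats the between-occasion variability term.** The protocol only says this term will be considered, and AVN007 contributes several PK days.
- **That the 240 mg cohort was dropped.** A count of 33 also fits a slip in the dose list with one subject lacking PK data. The study report is not available to settle it.

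**Conclusion.** The point holds as a defect in the dataset definition. Taken literally, it drops samples on 80 mg BID and, if the 14 days apply to the current dose, up to about 45% of week 8 samples on 160 mg under uniform visit timing. The loss of precision follows directly from that reading. Bias is conditional: none if intolerance is unrelated to exposure, and about 3–9% low in the illustrative range above (15% if exactly the highest fifth is lost). The bias is upward if exclusion falls on low exposures. Because the documents give no rate of 80 mg reductions, no rate of early stops and no correlation, no single figure can be defended. The missing early stoppers are a limitation of the schedule that redefining the dataset does not remove.

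**What to change.** - In section 6.13.7, redefine item 3 as every HD concentration at the dose actually taken, with actual dose history, dose times and sample times in the NONMEM file and no dose or minimum-duration restriction.
- Reconcile sections 6.6, 6.7, 6.13.7, 8 and Appendix A on which doses and visits feed the dataset, including the claim of periodic sampling against one occasion.
- Reconcile the AVN005 dose list and count with section 2.2.
- State as a limitation that participants who stop before week 8 and do not restart give no PK sample.

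This costs wording only: no added blood, visit or assay beyond samples already scheduled. A timed PK tube at the existing week 6 safety draw is optional and would need an amendment. It would mainly add those who stop between weeks 6 and 8, and would recover nobody who stopped before week 6.

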6.13.8 Subject Adherence Assessments

At each study visit, the site Investigator and/or Study Coordinator will assess the Subject's compliance with the study requirements. This will include checks of protocol compliance, including use of study drug, concomitant medications, and eDiary data, if applicable in order to assess the reliability of Subject-generated data. (If applicable, note that Subjects who fail to comply with the study requirements may be withdrawn from the study.)

7 MANAGEMENT OF ADVERSE EXPERIENCES

The following types of events were reported in Subjects taking SRX246 in Phase I studies: tachycardia, conjunctival hyperemia, upper abdominal pain, diarrhea, epigastric discomfort, gastroesophageal reflux, lip pain, nausea, vomiting, chest pain. Almost all of these were mild in intensity, and they were not dose related. Thus, at this point, there are no expected adverse events or special precautions that need to be given to trial Subjects.

Section 10 below also includes a detailed description of AE definitions, assessment/detection, grading (severity), potential relatedness to the investigational product, and reporting requirements. Below is a general strategy to guide modification or discontinuation of the study drug in response to AEs. The decision to decrease the dose of SRX246 or discontinue it altogether should be made by the site PI in consultation with the medical monitor should factor in potential relatedness of the AE to the study drug.

AE Grade	Management
≤ Grade 1 (mild)	No change in dose
Grade 2 (moderate)	*Hold until ≤ Grade 2. Resume at same dose level.
Grade 3 (severe)	*Hold until ≤ Grade 2. Resume at one dose level lower**
Grade 4 (life threatening or disabling)	Off protocol therapy

*Patients requiring a delay of > 1 week should go off therapy. Subjects can only hold medication once throughout the study. A Subject requiring a second hold should go off therapy.

**Patients requiring > two dose reductions should go off therapy.

Grade 1 AEs are defined as signs or symptoms that are easily tolerated. Grade 2 AEs are intense enough to interfere with usual activities. Grade 3 AEs interfere significantly with a Subject's ability to do work or his/her usual activities.

Worsening of Irritability and other Behavioral Symptoms

Since this study is expressly recruiting Subjects with irritability, which may coexist with anger, aggression, depression and suicidality, these symptoms represent expected adverse events due to the presence of HD, which will sometimes warrant intervention. Physicians who take care of HD and other movement disorder patients will have encountered these symptoms and will already be well versed in their management and in assessing the need for further assessment and intervention. Any Investigator who has completed a movement disorders fellowship will have had extensive training in management of suicidal ideation, worsening agitation and irritability, and other psychiatric symptoms in HD and other movement disorders. Training in the assessment and management of behavioral symptoms is provided to all HSG investigators at yearly HSG meetings as part of the Educational Program and will be included in the Investigator and Coordinator meetings. The site Investigator will be required to make a documented determination about whether clinical referral to a treating physician or acute intervention like hospitalization is warranted for AE s in this category that are grade 2 and above.

Investigators will be asked to characterize aggression AEs as:

- 1) Verbal aggression
- 2) Physical aggression: if physical: a) aggression toward self (self-injury, suicidal behavior); b) aggression toward others; c) aggression toward property; or d) aggression toward pets

Investigators will also be asked to report the outcome of these AEs:

- 1) Mental Health Referral
- 2) Emergency Room Visit
- 3) Psychiatric Hospitalization
- 4) Concomitant medications added

As part of the site initiation visit, sites will be given a worksheet to complete to document their local procedures for:

- 1) Escorting a patient from a study visit to the Emergency Room if needed due to exacerbation of behavioral symptoms
- 2) Setting up a rapid mental health referral (including names and contact for local psychiatrists, psychologists)
- 3) Facilitating a psychiatric hospitalization (contact names and numbers for local units with which they have a relationship)
- 4) Dealing with emergency phone call from Subject or care partner for worsening of behavioral symptoms

An Independent Medical Monitor (IMM) may also review all AEs, in a blinded fashion, on a periodic basis. In addition, the IMM will review all events that meet the regulatory definition of a Serious Adverse Event upon receipt of notification via the Electronic Data Capture (EDC) system.

Pregnancy

Pregnancy itself is not regarded as an AE unless there is a suspicion that the study drug may have interfered with the effectiveness of a contraceptive medication. However, the outcome of all pregnancies that occur during paternal or maternal exposure to study drug (spontaneous miscarriage, elective termination, normal birth or congenital abnormality) must be determined and documented even after the Subject has been withdrawn from the study. All reports of congenital abnormalities/birth defects are SAEs. Spontaneous miscarriages should also be reported and handled as SAEs. Elective abortions without complications should not be handled as AEs. Pregnancy and all outcomes of pregnancy must be reported to the Coordination Center.

